### **NON-TECHNICAL SUMMARY**

Provide a non-technical summary of the proposed research project that can be understood by IRB members with varied research backgrounds, including non-scientists and community members. The summary should include a brief statement of the **purpose of the research** and **related theory/data supporting** the intent of the study as well as a brief description of the **procedure(s) involving human subjects**. *This summary should not exceed ½ page.*

The goal of this research is to determine whether 10-weeks of exercise training can benefit asthmatic children and young adults with a history of exercise-induced bronchoconstriction (EIB). Physical activity is a double-edged sword for children and adults with asthma. On the one hand, exercise is a common trigger of wheezing (EIA—exercise induced asthma), occurring in as many as 80% of affected individuals. On the other hand, exercise and fitness training seem to benefit asthma control. The underlying causes responsible for EIA remain unknown. We will, for the first time, test hypotheses focused on mechanisms of exercise training, asthma and Exercise Induced Bronchoconstriction that involve the genomic changes of circulating white blood cells. We will also study an exciting newly discovered aspect of gene expression regulation in the white blood cells known as epigenetics: a process that takes place when genomic changes happen as a result of exposure to the environment. Our study is based on emerging exciting new data from this and other laboratories demonstrating that (1) white blood cells play an important role in bronchoconstriction[1,2] in children, (2) gene and cytokine expression in circulating white blood cells are abnormal in asthma,[3,4] and (3) brief exercise may change genomic and inflammatory-profiles of these cells.[5-7] Each participant will undergo a training regimen. The participants will come to our lab up to three times before the beginning of the training program, and up to three times immediately at the end of the exercise program to perform Exercise Fitness Session and Exercise Challenge Sessions. The visits may occur in any order, depending on the availability of the laboratory and timing. In the Exercise Fitness Session, the participant will perform a standard exercise test to determine fitness and will perform a series of pulmonary function tests. In addition, the participants will have two DXA scans to determine body composition (prior to

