**Specific Aims:** Using a novel exercise training treatment intervention designed specifically to promote sustainability and generalizability in children and adults with chronic diseases like asthma, we plan to:

*Primary Aims:*

1. Elucidate key abnormal genomic (including epigenetic) responses to brief exercise in leucocytes of children and adults with persistent asthma
2. Identify the effect of exercise training on the key genomic exercise response mechanisms in leucocytes in children and adults with persistent asthma

*Secondary Aim:*

3. Assess the clinical impact of exercise training in children and adults with persistent asthma on: (a) exercise induced airway inflammation, (b) asthma control, and (c) cardiorespiratory fitness and muscle adaptation.

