**Hypotheses:**

1. Leucocytes genomic, epigenetic, and functional regulation is abnormal in asthmatic individuals leading to a greater pro-inflammatory profile in response to a brief exercise challenge.
2. The exercise-training treatment will attenuate pro-inflammatory and intensify anti-inflammatory activity of leukocytes in response to brief exercise challenge.
3. The exercise-training treatment will diminish exercise-induced bronchoconstriction and its accompanying airway inflammation and improve asthma control.

**Impact:** Despite much recent progress in understanding asthma pathophysiology and the development of new therapies, the health care use associated with asthma, and the disruptions it causes to family and community life, have not decreased substantially. The link between physical activity and asthma is strong, but remains enigmatic. Physical activity is a “double-edged sword” for the people with asthma. On the one hand, exercise is a common trigger of wheezing in asthma, occurring, in some studies, in as many as 80% of affected children. On the other hand, exercise and fitness training seem to benefit asthma control in many affected children.

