## B. Statistical Analysis Plan

1. **Variables of Interest** - Clearly identify the primary outcome(s) and key factor(s) of interest.
2. **Statistical goal** - State the statistical goal(s) of the study (e.g., Comparison of group means, estimation of the proportion of success, estimation of variability for future study design, etc.).
3. **Statistical approach** - Describe the statistical approach(es) to be used to address the study's statistical goal(s) (e.g., T-test to compare means, confidence interval estimate(s), etc.). *Note: Required for ICTS SRC review.*
4. **Secondary analyses** - Clearly state any secondary analyses to be performed including secondary outcomes and comparison groups along with the statistical methods that will be used to perform the secondary analyses. *Note: Required for ICTS SRC review.*

***If a statistical analysis plan is not appropriate for your study design, please describe a non-statistical plan for assessing your study results.***

***Aim 1: Elucidate key abnormal genomic and epigenetic responses to brief exercise in leukocytes of children and adults with moderate-to-severe asthma.***

***Aim 2: Identify the effect of training on the key genomic and epigenetic exercise response mechanisms in leukocytes in children and adults with moderate-to-severe asthma.***

Genomic expression profile is the **primary outcome variable** for Aims 1 and 2. Gene expression data will be normalized, log-transformed, and quality-checked and filtered across all arrays from all study subjects. Pre- to end-exercise change and before- to after-training change will be calculated for each subject and each probe set. Probe sets that pass filtration and belong to

selected functional pathways will be examined for group difference using 2-sample t-test and further adjusted with false discovery rate (FDR) controlling adjustments as described by Benjamini and Hochberg.

Leukocyte cell-function profile is the **secondary outcome variable** for Aims 1 and 2. Each outcome variable will be treated as an individual hypothesis. The primary analysis will apply 2-sample t-test to examine group difference in exercise effect and in training effect. The secondary analysis will utilize mixed model to evaluate group difference in training and exercise effect together, adjusting for possible confounding factors such as gender, BMI percentile, and fitness level.

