**Aim 3:** *Assess the clinical impact of exercise training in children and adults with persistent asthma on: (a) exercise induced airway inflammation, (b) asthma control, and (c) cardiorespiratory fitness and muscle adaptation.*

Outcomes from Aim 3 are considered as secondary outcome variables. We will apply paired t-tests for before- to after-training change. Furthermore, we will employ linear regression model to examine the effect of covariates such as gender, asthma severity (ACQ), and lean muscle tissue response to exercise-training (as determined by DXA).

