8. Explain **how the overall target sample size was determined** (e.g., power analysis; precision estimation).

9. Demonstrate that the **target sample size will be sufficient** to achieve the study goal and should coincide with the statistical approach **described in Section 3B**.

10. **Sources and information** of assumed group effects and variability should be supplied (e.g., pilot data; data from related literature).

To accomplish our aims, we will recruit 70 asthmatics and 70 gender-, age- and fitness-matched controls (as noted, below the 50th percentile of appropriate normative data) to participate in the training course. Given an anticipated dropout rate (based on our experience in recruiting subjects in this region) of about 10-15%, we expect to have complete samples around 60 participants in each group of children. The power analyses were based on PASS 2008 (Hintze, J. (2008). NCSS, LLC. Kaysville, Utah. [www.ncss.com](http://www.ncss.com)).

For the adult groups we will recruit 50 asthmatics and 50 gender, age and fitness-matched controls. We expect to have complete samples around 40 participants in each group.

For the primary outcome in gene expression, we will include about 3000 probe sets belonging to functional pathways of interest in asthma and exercise, as described above and in the Preliminary Studies Section. After filtration, around 1000 to 2000 probe sets will be left for analysis. Table 3 in the Human Subjects Section shows the power and effect size that can be detected from microarray data using a 2-sided 2-sample t-test for a range of: (1) probe sets **to examine** and (2) significant probe sets **to detect** (with FDR at 0.05 level). With the same power, a smaller effect size can be detected with a larger sample size. Effect size is defined as the expected log-transformed group difference divided by the within-group standard deviation. Our previous data showed that about 5% of the probe sets have an effect size over 0.9.

Table 4 shows the power analysis for the secondary outcome variables (e.g., in Aim 1, leukocyte function; in Aim 2, change in exhaled NO after the exercise challenge). The effect size is defined as the expected group difference divided by the within-group standard deviation for 2-sample t-test and as the mean difference between before- and after-training divided by the standard deviation of the difference for paired t-test.

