## B. Inclusion and Exclusion Criteria

1. Describe the **characteristics and provide justification** for inclusion of the proposed subject population. At a minimum include information about the age and gender of the study population.
2. Describe **different subject groups** (e.g., students and teachers; control group and treatment group(s), children and adults) separately.

The study population will consist of 60 children with Asthma (boys and girls, 8-17y/o) and 40 adults with Asthma (men and women, 18 yrs -35y/o) who: have been determined to be in good health by pre-participation sports physical performed at PERC, have no evidence of disease or disability that would impair participation in a vigorous physical activity program, have been diagnosed with persistent asthma according to criteria by NHLBI, have a clinical history of suggestive of exercise induced bronchoconstriction, have less than 50% fitness as determined from our own normative data collected in our lab (N=95), and with BMI percentile < 95th.

The control groups will be age, gender, and fitness matched with asthmatic participants, and consist of 60 children (boys and girls, 8-17yrs) and 40 adults (men and women, 18yrs -35y/o) who have been determined to be in good health by preparticipation history and physical examination performed at PERC, have no evidence of disease or disability that would impair performance of cycle ergometer exercise, and BMI < 95th percentile.

3. Provide the **inclusion and/or exclusion criteria** for the proposed subject population, as applicable.

[ ] Not applicable – This is not a clinical investigation and/or the characteristics of the population sufficiently describe the proposed subject population.

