**Inclusion criteria Subjects with Asthma**

- Determined to be in good health by preparticipation history and physical examination performed at PERC
- No evidence of disease or disability that would impair participation in a vigorous physical activity program
- Diagnosed with persistent asthma according to criteria by NHLBI
- Clinical history suggestive of exercise induced bronchoconstriction
- VO2max <55 ml O2/kg/min and habitual physical activity corresponding to lifestyles from sedentary to moderately physically active, with exclusion of intense physical training
- BMI less than 95th percentile

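### Aim 3's paired t-tests in an all-trained sample support change over the training period, not the clinical impact of training; peak VO2 may also carry regression to the mean

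*Protocol*

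**What the plan says.** **Who trains.** The Non-Technical Summary says "Each participant will undergo a training regimen". The sample-size text in Section 4A recruits the child controls as well as the children with asthma, below the 50th "percentile of appropriate normative data) to participate in the training course". No untrained, waiting-list or delayed-training group with asthma is described.

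**What is tested.** Section 3B gives the Aim 3 analysis: "We will apply paired t-tests for before- to after-training change", followed by a linear regression on covariates. Table 1 puts the two assessments in weeks 1 and 12.

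**What is claimed.** Aim 3 is to "Assess the clinical impact of exercise training in children and adults with persistent asthma on" airway inflammation, asthma control, and fitness and muscle outcomes. Hypothesis 3 is "The exercise-training treatment will diminish exercise-induced bronchoconstriction and its accompanying airway inflammation and improve asthma control".

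**Who qualifies on fitness.** The population description in Section 4B says participants with asthma "have less than 50% fitness as determined from our own normative data collected in our lab (N=95". I read this as the 50th percentile, in line with Section 4A. The listed inclusion criteria, for asthma and control subjects alike, contain no percentile cut and instead require "VO 2 max <55 ml O 2 /kg/min and habitual physical activity" short of intense training. Table 1 shows one ramp test before training and no separate screening test.

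**The concern.** A paired t-test asks whether the mean of after minus before is zero. It does not ask whether training caused the difference. With no untrained participants with asthma, anything else that moves between week 1 and week 12 is credited to training: familiarity with the tests, season and, in children aged 8 to 17, growth. The covariate regression cannot separate these, because everyone in it trained.

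Peak VO2, the fitness measure for Aim 3(c), has a possible additional bias built into recruitment. If people are admitted because a ramp test was low, and that test is also their baseline, part of the low value is chance and will not recur at retest. The average then rises with no training effect.

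At stake is the statement of clinical benefit. Aim 3 is secondary, but it and Hypothesis 3 carry the question of whether training helps people with asthma.

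**Working it through.** **1. The plan's own figures.** Table 4 gives detectable effects for the two-sided paired t-test, defined in Section 4A as mean change divided by the SD of change. Noncentral-t power at two-sided alpha 0.05 (alpha is not stated for this table) reproduces all nine paired entries to three decimals, for example 0.454 for 40 participants and 0.368 for 60 at 80% power. The paired power table is sound. The issue is what the test can show.

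**2. Inputs for peak VO2.**
- Completers: 60 children and 40 adults per group (Section 4A).
- True training effect: zero, to find the false-positive rate.
- Test-retest correlation r: not in the protocol, so assumed at 0.95, 0.90 and 0.80.
- Position of the fitness cut, c, in SDs from the candidates' mean: not in the protocol, so three cases are shown.
- The qualifying ramp test is the baseline test: assumed. Table 1 suggests it but does not say so.

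**3. Formulas.** For standardised baseline X and retest with correlation r, selecting X < c, let h = φ(c)/Φ(c).
- Expected rise: (1 − r) × h
- Variance of X after selection: v = 1 − c·h − h²
- Variance of change: (1 − r)² × v + 1 − r²
- Spurious effect size: rise / SD of change
- Rejection rate: power of the paired t-test at that effect size

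**4. One case in full** (c = 0, r = 0.80).
- h = 0.3989/0.5 = 0.798
- Rise = 0.20 × 0.798 = 0.160 SD
- v = 1 − 0.798² = 0.363
- Variance of change = 0.04 × 0.363 + 0.36 = 0.3745, so its SD is 0.612
- Effect size = 0.160/0.612 = 0.26
- Rejection rate: 36% with 40 participants, 51% with 60

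**5. All cases, no training effect.**

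| Cut | r | Rise (SD) | Effect size | n = 40 | n = 60 |
|---|---|---|---|---|---|
| Candidates' own median (c = 0) | 0.95 | 0.04 | 0.13 | 12% | 16% |
| | 0.90 | 0.08 | 0.18 | 20% | 28% |
| | 0.80 | 0.16 | 0.26 | 36% | 51% |
| 0.5 SD above candidates' mean | 0.95 | 0.03 | 0.08 | 8% | 9.5% |
| | 0.90 | 0.05 | 0.12 | 11% | 14% |
| | 0.80 | 0.10 | 0.17 | 18% | 24% |
| Only the ceiling of 55 binds, assumed 1.5 to 2 SD above the mean | 0.95 to 0.80 | at most 0.03 | at most 0.04 | 5 to 6% | 5 to 6% |

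Simulation of the first case (20,000 replicates) gave 13%, 20% and 36% with 40 participants and 16%, 28% and 51% with 60.

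**6. Scale.** With the cut at the candidates' median, the spurious effect of 0.13 to 0.26 is about 35 to 71% of the 0.368 that Table 4 counts as detectable at 80% power with 60 participants (0.127/0.368 and 0.261/0.368).

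**7. Source of the inflation.** In the same simulation, a two-sample comparison of changes between two equally selected groups, with no training effect in either, rejected in 4.8 to 5.2% of replicates. The excess comes from having no comparator.

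**8. What has no figure.** The protocol gives nothing from which to size growth, familiarity or season. That part of the point rests on the design alone.

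**The case against.** The before-after component is openly uncontrolled, and the Aim 3 analysis sentence already speaks of change around training. For that null hypothesis the paired test holds its level. A causal hypothesis is also not yet a reported conclusion. This is fair as to the test. It does not answer the wording of Aim 3 and Hypothesis 3, which the test is meant to serve and which attribute the result to training.

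A reader might infer that regression to the mean affects all of Aim 3. The documents do not support that. Fitness selection acts directly only on peak VO2. Airway inflammation and asthma control are not selected on fitness, and Hypothesis 3 does not mention peak VO2. The exclusion of people with more than two asthma attacks a week would, if anything, push asthma control toward apparent worsening.

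The size is also uncertain, for three reasons:
- The 50th percentile belongs to the laboratory's normative sample of 95, not to candidates with asthma. Section 1 says fitness is impaired in children with asthma, so the cut probably lies above their own median and removes fewer people. This is why the middle case in the table is needed.
- The listed criteria give only the ceiling of 55, under which inflation almost vanishes.
- No passage says that the qualifying test is the baseline. A separate qualifying test would remove most of the effect.

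All three stand and make the peak VO2 part conditional. None touches the point about attribution.

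**Conclusion.** The point holds in two parts of different strength.

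For all Aim 3 outcomes, the paired tests support change over the training period and nothing more. This follows from the text: everyone trains, and Aim 3 has no comparator. The healthy controls do not supply one, since they train too and the Aim 3 analysis does not use them.

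For peak VO2 only, the nominal 5% test may be inflated. The range runs from about 5% (ceiling only) to 36% with 40 participants or 51% with 60 (cut at the candidates' median, r = 0.80). It rests on assumed correlations, an assumed position of the cut, and the assumption that one ramp test both qualifies and serves as baseline.

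A reader might go further and expect a significant rise in peak VO2 even if training does nothing. The figures do not support that: for r of 0.90 or more, no case exceeds 28%, and only one cell in the table passes 50%. Nor should the wording of Aim 2, "Identify the effect of training on the key genomic and epigenetic exercise response mechanisms", be read into this point. Aim 2 is analysed by a two-sample test, although that contrast does not isolate training either, because both groups train.

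**What to change.** 1. In Aim 3, Hypothesis 3 and the Aim 3 analysis text, state that the paired tests estimate change over the training period and that this change is not attributed to training.
2. Reconcile the fitness criterion in Section 4A and the Section 4B population description with the listed inclusion criteria for both groups, and state whether the qualifying ramp test is also the baseline.
3. If it is, report the peak VO2 change with a regression-to-the-mean sensitivity analysis over a stated range of test-retest reliability.
4. Label any analysis of change on session attendance, which Table 1 already records, as exploratory. Attendance is not randomised and may reflect motivation or asthma status.

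The cost is a weaker claim on a secondary aim and a small extra analysis. No arm, participant or visit is added.

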#### **SECTION 4: SUBJECTS (PERSONS/CHARTS/RECORDS/SPECIMENS)**

##### **A. Number of Subjects (Charts/Records/Biospecimens)**

1. Indicate the **maximum number of subjects to be recruited/consented** on this UCI protocol. This is the number of potential subjects you may need to recruit to obtain your target sample size. This number should include projected **screen failures and early withdrawals**. *Note: The IRB considers individuals who sign the consent form to be "enrolled" in the research.*
2. For **Mail/Internet surveys** include the number of people directly solicited.
3. If the study involves use of **existing charts, records, biospecimens**, specify the maximum number that will be reviewed/tested to compile the data or the sample population necessary to address the research question.

The maximum number of subjects to be recruited/consented on this protocol is 240. This number includes screen failure and early withdrawals (see table 2 for breakdown in subjects for each group).

4. Of the maximum number of subjects listed above, indicate the **target sample size** for the study. This is the number of subjects expected to complete the study or the number necessary to address the research question.
5. For *social/behavioral research*, the maximum sample size is often similar to the target sample size. If the **maximum sample size** is significantly greater (i.e.,  $\geq 1.5x$ ) than the **target sample size** provide a justification.
6. For studies where multiple groups of subjects will be evaluated, **provide a breakdown per group** (e.g. controls vs. experimental subjects; children vs. adults; by age group).

Of the maximum number of participants, our target sample size is 200. Below is a table with a breakdown in the number of participants per group.

Table 2: Subject number break down per group for maximum number to be recruited and target number of participants.

	Maximum to be Recruited		Target Participants	
	Control	Asthma	Control	Asthma
Mid and late pubertal boys (Tanner 3-5) age 8 - 17 years	35	35	30	30
Mid and late pubertal girls (Tanner 3-5) age 8 - 17 years	35	35	30	30
Young adult women aged 18-35	25	25	20	20
young adult men aged 18-35	25	25	20	20
Total number of subjects	240		200	

7. For **multi-center research**, indicate the overall sample size for the entire study (across all sites).

Not applicable - This study is not a multi-center research study.

8. Explain **how the overall target sample size was determined** (e.g., power analysis; precision estimation).

9. Demonstrate that the **target sample size will be sufficient** to achieve the study goal and should coincide with the statistical approach **described in Section 3B**.

10. **Sources and information** of assumed group effects and variability should be supplied (e.g., pilot data; data from related literature).

To accomplish our aims, we will recruit 70 asthmatics and 70 gender-, age- and fitness-matched controls (as noted, below the 50th percentile of appropriate normative data) to participate in the training course. Given an anticipated dropout rate (based on our experience in recruiting subjects in this region) of about 10-15%, we expect to have complete samples around 60 participants in each group of children. The power analyses were based on PASS 2008 (Hintze, J. (2008). NCSS, LLC. Kaysville, Utah. [www.ncss.com](http://www.ncss.com)).

For the adult groups we will recruit 50 asthmatics and 50 gender, age and fitness-matched controls. We expect to have complete samples around 40 participants in each group.

For the primary outcome in gene expression, we will include about 3000 probe sets belonging to functional pathways of interest in asthma and exercise, as described above and in the Preliminary Studies Section. After filtration, around 1000 to 2000 probe sets will be left for analysis. Table 3 in the Human Subjects Section shows the power and effect size that can be detected from microarray data using a 2-sided 2-sample t-test for a range of: (1) probe sets **to examine** and (2) significant probe sets **to detect** (with FDR at 0.05 level). With the same power, a smaller effect size can be detected with a larger sample size. Effect size is defined as the expected log-transformed group difference divided by the within-group standard deviation. Our previous data showed that about 5% of the probe sets have an effect size over 0.9.

Table 4 shows the power analysis for the secondary outcome variables (e.g., in Aim 1, leukocyte function; in Aim 2, change in exhaled NO after the exercise challenge). The effect size is defined as the expected group difference divided by the within-group standard deviation for 2-sample t-test and as the mean difference between before- and after-training divided by the standard deviation of the difference for paired t-test.

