**Table 3. Power Analysis for the Primary Outcome Variables**

Number of Probe Sets to Examine		1000				2000			
Number of Probe Sets to Detect		10	50	100	300	10	50	100	300
Sample Size	Power	Effect Size							
40 per group	90%	1.1	1.0	0.9	0.8	1.2	1.0	1.0	0.9
	80%	1.0	0.9	0.8	0.7	1.1	1.0	0.9	0.8
	70%	1.0	0.8	0.8	0.7	1.0	0.9	0.8	0.7
60 per group	90%	0.9	0.8	0.8	0.7	0.9	0.8	0.8	0.7
	80%	0.8	0.7	0.7	0.6	0.9	0.8	0.7	0.7
	70%	0.8	0.7	0.6	0.5	0.8	0.7	0.7	0.6

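### Table 3 does not give the power of the Benjamini-Hochberg analysis named in Section 3B: coarse rounding, and a planning formula less strict than that procedure, leave 11 of 48 entries at least 5 points short of their stated power (minor; sample size unaffected)

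*Protocol*

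**What the plan says.** Section 3B (Statistical Analysis Plan), Aims 1 and 2, makes gene expression the primary outcome. Probe sets that pass filtering are compared between groups with a 2-sample t-test, and the results are "further adjusted with false discovery rate (FDR) controlling adjustments as described by Benjamini and Hochberg".

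Section 4A (Number of Subjects) justifies the sample size. It states that "After filtration, around 1000 to 2000 probe sets will be left for analysis" and refers to a table that "shows the power and effect size that can be detected from microarray data using a 2-sided 2-sample t-test", "with FDR at 0.05 level". The expected completers are 60 per group for children ("we expect to have complete samples around 60 participants in each group of children") and 40 per group for adults ("We expect to have complete samples around 40 participants in each group"). As the planning signal, it cites earlier data in which about 5% of probe sets had an effect size above 0.9. The software is PASS 2008. No FDR formula is given.

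"Table 3. Power Analysis for the Primary Outcome Variables" crosses two sample sizes, three powers (90, 80 and 70%) and eight settings: 1000 or 2000 probe sets examined, with the row "Number of Probe Sets to Detect" set at 10, 50, 100 or 300. Its 48 effect sizes have one decimal. Table 4, for the secondary outcomes, has three.

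**The concern.** The form's own instructions in Section 4A ask that the sample-size justification agree with the statistical approach in Section 3B. A reader will therefore take each Table 3 entry as the group difference that the BH-adjusted t-test detects with the power shown for that row.

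Two features prevent this. First, the entries fit a formula whose per-test significance level is more generous than the level BH applies when many probe sets differ. Second, effect sizes are rounded to the nearest 0.1. In this range 0.1 is a large step: where the value was rounded down, the printed effect can have clearly less than the stated power.

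Table 3 is the only power statement for the primary outcome, so what is at stake is how small a difference the study may claim to be able to detect.

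**Working it through.** **Inputs.** All are from Section 4A, Table 3 and Section 3B: 2-sided 2-sample t-test, n = 40 or 60 per group, FDR q = 0.05, m = 1000 or 2000 probe sets examined, K = 10, 50, 100 or 300 to detect, powers P = 90, 80 and 70%. Assumptions not in the protocol: independent probe sets, one common effect size, and K equal to the number that truly differ. Power means average power over those K. It comes from the noncentral t with 2n − 2 degrees of freedom and noncentrality d·√(n/2).

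**Step 1: reproduce Table 3.** Take the per-test level as

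α = K·P·q / [(m − K)(1 − q)],

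which uses the number of true nulls, m − K, as if it were known. Solving for d and rounding to one decimal matches 48 of 48 entries. The same expression without the factor (1 − q) also matches 48 of 48, so the exact formula is not identified, but both use m − K. Using the BH level instead,

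α = K·P·q / [m − q(m − K)],

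matches 43 of 48.

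**Step 2: size of the formula difference.** For 300 of 1000 at 70% power:

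- formula: 300 × 0.70 × 0.05 / (700 × 0.95) = 10.5 / 665 = 0.0158, giving d = 0.543 with 60 per group;
- BH: 10.5 / (1000 − 35) = 10.5 / 965 = 0.0109, giving d = 0.568;
- ratio of levels: 665 / 965 = 0.69.

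**Step 3: BH power at the printed effect.** Solve α = q·[K·power(α) + (m − K)·α] / m for each cell. The 11 cells at least 5 points short are:

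| n per group | K of m | Stated power | Printed d | d before rounding (formula) | d needed under BH | BH power at printed d |
|---|---|---|---|---|---|---|
| 40 | 300 of 1000 | 90% | 0.8 | 0.820 | 0.853 | 84.8% |
| 40 | 100 of 1000 | 80% | 0.8 | 0.842 | 0.851 | 72.1% |
| 40 | 300 of 1000 | 80% | 0.7 | 0.730 | 0.762 | 69.8% |
| 40 | 50 of 1000 | 70% | 0.8 | 0.836 | 0.840 | 62.3% |
| 40 | 100 of 2000 | 70% | 0.8 | 0.836 | 0.840 | 62.3% |
| 40 | 300 of 2000 | 70% | 0.7 | 0.743 | 0.757 | 58.5% |
| 60 | 50 of 2000 | 90% | 0.8 | 0.843 | 0.845 | 84.7% |
| 60 | 50 of 1000 | 80% | 0.7 | 0.727 | 0.730 | 74.5% |
| 60 | 100 of 2000 | 80% | 0.7 | 0.727 | 0.730 | 74.5% |
| 60 | 100 of 1000 | 70% | 0.6 | 0.631 | 0.638 | 60.9% |
| 60 | 300 of 1000 | 70% | 0.5 | 0.543 | 0.568 | 52.0% |

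Simulating the BH step-up procedure in the last cell also gave 52.0% (standard error 0.1 point). BH power is above the stated power in 19 of 48 cells, for example 85.6% for 80% at 40 per group, 50 of 2000, effect 1.0.

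**Step 4: separate the two causes.** Count the cells more than 2 points short:

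- both together: 21;
- rounding only (formula's threshold, printed effects): 17;
- formula only (BH at unrounded effects): 8.

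In the worst cell, rounding alone leaves 59% (61% if the threshold is held fixed), the formula alone 64%, and both 52%. The formula alone costs 5 points or more in only two cells, 300 of 1000 at 70% power with 40 and with 60 per group. At 10 or 50 probe sets to detect it costs under 1 point.

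**Step 5: entries wrong even at one decimal.** Exact BH effects rounded to 0.1 differ from the print in five cells, each printed 0.1 too small: 40 per group, 300 of 1000 at 90% and at 80%; 40 per group, 100 of 1000 at 80%; 40 per group, 300 of 2000 at 70%; 60 per group, 300 of 1000 at 70%.

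**Step 6: the plan's anchor.** With 5% of probe sets at effect 0.9 (50 of 1000 or 100 of 2000), BH power is 79.5% with 40 per group and 96.5% with 60.

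**The case against.** The strongest reply is that Table 3 is correct on its own terms. It promises effect sizes at an FDR of 0.05, every entry follows from a formula that sets the FDR at 0.05, and one decimal is simply the table's precision. That stands as far as it goes: this is not a slip of arithmetic. It does not answer the mismatch with Section 3B, because the named procedure does not deliver the stated power at the printed effects.

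Four further points stand and limit the finding:

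- The formula is inferred, and two variants fit equally well.
- Rounding runs both ways: against the unrounded formula values, 24 entries are rounded up and 24 down.
- The worst cell is far from the planning scenario, since it supposes that 30% of probe sets differ. However, four of the 11 short cells do lie in the 5% columns (50 of 1000 and 100 of 2000), where rounding is almost the whole cause.
- The numbers rest on independence and a common effect, which the protocol does not state.

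Reading K as the expected number of detections does not rescue the worst cell. BH power there is still 58.6%, and that reading reproduces only 39 of 48 entries.

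A reader might also see a contradiction where one effect size appears in two adjacent power rows, such as 1.0 at both 90% and 80% for 40 per group and 50 of 2000. These are rounding ties. The unrounded values are 1.045 and 0.952, and the print is conservative for the 80% row.

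**Conclusion.** The point holds as a minor one. Table 3 misstates the power of the Section 3B analysis: at least 5 points too high in 11 of 48 cells, at worst 52% for a stated 70%, and too low in 19. One-decimal rounding is the larger cause. The known-null formula adds to it mainly where 300 probe sets are to be detected, above all 300 of 1000. The figures assume independent probe sets, a common effect and K truly different probe sets.

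A reader might infer that the study is underpowered for its primary outcome. The protocol does not support that. Its own anchor gives 79.5% power with 40 per group, in line with the 0.9 printed for 80%, and 96.5% with 60. Nor does the evidence make the formula the main fault.

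**What to change.** Recompute Table 3 for the 2-sample t-test with BH at FDR 0.05. State the formula, the meaning of K, and the assumptions of independence and a common effect. Print effect sizes to two decimals, rounded up. For 300 of 1000 the entries at 90 / 80 / 70% power become:

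- 40 per group: 0.86 / 0.77 / 0.71 (now 0.8 / 0.7 / 0.7);
- 60 per group: 0.70 / 0.62 / 0.57 (now 0.7 / 0.6 / 0.5).

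Keep the sample size. The cost is one recalculated table and a sentence or two of text. Some detectable effects will look slightly less favourable and others slightly more. Enrolment, procedures and the planned analysis do not change.
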